2.4.4.2 Analyses of secondary efficacy endpoints

Secondary efficacy endpoints defined in Section 2.1.3.2 will be analyzed in the ITT population and separately for the T1DM patients, using all post-baseline data available during the main 6-month randomized period (for analyses at Week 26) or the 12-month randomized period (for analyses at Week 52).

2.4.4.2.1 Continuous endpoints

All continuous secondary efficacy endpoints (except for 7-point SMPG profiles per time-point) will be analyzed using a similar multiple imputation approach in two parts, as for the primary efficacy endpoint, followed by a similar ANCOVA model (as described in Section 2.4.4.1.1).

- At Week 26:
 - Missing data in patients who prematurely discontinued IMP during the main 6-month randomized period will be imputed using a model including only the treatment group as predictor (Part 1),

- Missing data in patients who completed the main 6-month treatment period will be imputed in step 1 using a model including the continuous fixed covariates of the baseline value and the change from baseline at Week 12 and Week 26, in step 2 using a model including the fixed categorical effects of the treatment group, the randomization strata of geographical region and type of diabetes (Europe T1DM, US T1DM, US T2DM, Japan T1DM), screening HbA1c (<8%, ≥8%) (except when analyzing the change in HbA1c) and prior use of NovoLog/NovoRapid (Yes, No), as well as the continuous fixed covariates of the baseline value and the changes from baseline at Week 12 and Week 26 (Part 2).
- At Week 52 :
 - Missing data in patients who prematurely discontinued IMP during the 12-month randomized period will be imputed using a model including only the treatment group as predictor (Part 1),
 - Missing data in patients who completed the 12-month treatment period will be imputed in step 1 using a model including the continuous fixed covariates of the baseline value as well as the changes from baseline at Week 12, Week 26, Week 40 (except for SMPG endpoints) and Week 52, in step 2 using a model including the fixed categorical effects of the treatment group, the randomization strata of geographical region and type of diabetes (Europe T1DM, US T1DM, US T2DM, Japan T1DM), screening HbA1c (<8%, ≥8%) (except when analyzing the change in HbA1c) and prior use of NovoLog/NovoRapid (Yes, No), as well as the continuous fixed covariates of the baseline value and the changes from baseline at Week 12, Week 26, Week 40 (except for SMPG endpoints) and Week 52 (Part 2).

For 7-point SMPG profiles per time-point, only descriptive statistics and graphs will be provided.

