Data obtained after the above imputations will be analyzed using an analysis of covariance (ANCOVA) of the change in HbA1c from baseline to Week 26, including the fixed categorical effects of treatment group (SAR341402, NovoLog/NovoRapid), randomization strata, as well as the continuous fixed covariate of baseline value.

The adjusted least squares mean (LS mean) of the change in HbA1c from baseline to Week 26 for each treatment group (SAR341402, NovoLog/NovoRapid) will be estimated, as well as the between-group LS mean difference of SAR341402 versus NovoLog/NovoRapid, with the corresponding standard errors and 2-sided 95% CIs.

Non-inferiority will be demonstrated if the upper bound of the 2-sided 95% CI of the difference between SAR341402 and NovoLog/NovoRapid on the ITT population is <0.3%. If non-inferiority of SAR341402 over NovoLog/NovoRapid is demonstrated, using a hierarchical step-down testing procedure, the following additional analysis will be performed (not as primary objective): the inverse non-inferiority (of NovoLog/NovoRapid over SAR341402) will be tested looking at the lower bound of the 2-sided 95% CI of the difference between SAR341402 and NovoLog/NovoRapid in the ITT population. Non-inferiority of NovoLog/NovoRapid over SAR341402 will be demonstrated if the lower bound is >-0.3%. If SAR341402 is shown to be non-inferior to NovoLog/NovoRapid and NovoLog/NovoRapid non-inferior to SAR341402, similar efficacy (equivalence) of SAR341402 and NovoLog/NovoRapid will be assumed.

Analysis of secondary endpoints:

Secondary efficacy endpoints will be analyzed in the ITT population, using all post-baseline data available (ITT estimand).

A similar multiple imputation approach in two parts, as for the primary efficacy endpoint, will be used for continuous secondary efficacy endpoints (change in HbA1c from baseline to Week 52, and change in FPG, mean 24 hour plasma glucose concentration, and postprandial plasma glucose excursions from baseline to Week 26 and Week 52), followed by a similar ANCOVA model.

The categorical secondary efficacy endpoint (HbA1c responders) will be analyzed using a logistic regression model with fixed-effect term for treatment group (SAR341402, NovoLog/NovoRapid) and the randomization strata. Patients without assessment at Week 26 (or Week 52 for the analysis at Week 52) will be considered as failure.

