- 2. Missing data in patients who completed the main 6-month treatment period will be imputed separately, using a model estimated solely from data observed in other patients who completed the main 6-month treatment period and have the measurement for the primary endpoint at Week 26. Since in general, the missing pattern will not be monotone, a two-step approach will be used:
- Step 1: the Markov Chain Monte Carlo (MCMC) method will be used in conjunction with the IMPUTE=MONOTONE option to create an imputed data set with a monotone missing pattern. The imputation model will include the continuous fixed covariates of the baseline HbA1c value as well as the changes from baseline in HbA1c at Week 12 and Week 26.
- Step 2: using the monotone data set from step 1, missing data will be imputed using the regression method. The imputation model will include the fixed categorical effects of the treatment group, the randomization strata geographical region and type of diabetes (Europe T1DM, US T1DM, US T2DM, Japan T1DM), screening HbA1c (<8%, ≥8%) (except when analyzing the change in HbA1c) and prior use of NovoLog/NovoRapid (Yes, No), as well as the continuous fixed covariates of the baseline HbA1c value and the changes from baseline in HbA1c at Week 12 and Week 26.

Missing values will be imputed 10 000 times. Completed datasets from the two parts detailed above will be combined into a single dataset. Each completed dataset will be analyzed using an analysis of covariance (ANCOVA) of the change in HbA1c from baseline to Week 26, including the fixed categorical effects of treatment group (SAR341402, NovoLog/NovoRapid), the randomization strata geographical region and type of diabetes (Europe T1DM, US T1DM,

US T2DM, Japan T1DM), screening HbA1c (<8%, $\ge8\%$) (except when analyzing the change in HbA1c) and prior use of NovoLog/NovoRapid (Yes, No), as well as the continuous fixed covariate of baseline value. Results from the 10 000 analyses will be combined using Rubin's formula.

The adjusted least squares (LS) mean of the change in HbA1c from baseline to Week 26 for each treatment group (SAR341402, NovoLog/NovoRapid) will be estimated, as well as the between-group LS mean difference of SAR341402 versus NovoLog/NovoRapid, with the corresponding standard errors and 2-sided 95% CIs.

Non-inferiority will be demonstrated if the upper bound of the 2-sided 95% CI of the difference between SAR341402 and NovoLog/NovoRapid on the ITT population is <0.3%.

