11.4.2.2 Analyses of secondary efficacy endpoints

All secondary efficacy endpoints (as defined in Section 9.2.2) will be analyzed in the ITT population, for descriptive purpose only (no formal statistical testing). Separate analyses will be performed for the main 6-month and the 12-month periods.

All continuous secondary efficacy endpoints will be analyzed using a similar multiple imputation approach in two parts, as for the primary efficacy endpoint, followed by a similar ANCOVA model (as described in Section 11.4.2.1).

The categorical secondary endpoint (HbA1c responders) will be analyzed using a logistic regression model adjusted on the randomization strata of geographical region and type of diabetes (Europe T1DM, US T1DM, US T2DM, Japan T1DM), screening HbA1c (<8%, ≥8%), and prior use of NovoLog/NovoRapid (Yes, No). Patients without assessment at Week 26 (or Week 52 for the analysis at Week 52) will be considered as failure.

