1.6 STATISTICAL MODIFICATIONS MADE IN THE STATISTICAL ANALYSIS PLAN

Not applicable.

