Missing data in patients who completed the main 6-month treatment period will be imputed separately, using a model estimated solely from data observed in other patients who completed the main 6-month treatment period and have the measurement for the primary endpoint at Week 26. Since in general, the missing pattern will not be monotone, a two-step approach will be used:

- Step 1: the Markov Chain Monte Carlo (MCMC) method will be used in conjunction with the IMPUTE=MONOTONE option to create an imputed data set with a monotone missing pattern. The imputation model will include the continuous fixed covariates of the baseline HbA1c value as well as the changes from baseline in HbA1c at Week 12 and Week 26.
- Step 2: using the monotone data set from step 1, missing data will be imputed using the regression method. The imputation model will include the fixed categorical effects of the treatment group, the randomization strata of geographical region and type of diabetes (Europe T1DM, US T1DM, US T2DM, Japan T1DM) and prior use of NovoLog/NovoRapid (Yes, No), as well as the continuous fixed covariates of the baseline HbA1c value and the changes from baseline in HbA1c at Week 12 and Week 26.

Missing values will be imputed 10,000 times. Completed datasets from the two parts detailed above will be combined into a single dataset. Each completed dataset will be analyzed using an analysis of covariance (ANCOVA) of the change in HbA1c from baseline to Week 26, including the fixed categorical effects of treatment group (SAR341402, NovoLog/NovoRapid), the randomization strata of geographical region and type of diabetes (Europe T1DM, US T1DM, US T2DM, Japan T1DM) and prior use of NovoLog/NovoRapid (Yes, No), as well as the continuous fixed covariate of baseline value. Results from the 10,000 analyses will be combined using Rubin's formula (MIANALYZE procedure in SAS).

Statistical Analysis Plan SAR314102-EFC15081 - insulin aspart 28-Feb-2018 Version number: 1

The adjusted least squares (LS) mean of the change in HbA1c from baseline to Week 26 for each treatment group (SAR341402, NovoLog/NovoRapid) will be estimated, as well as the between-group LS mean difference of SAR341402 versus NovoLog/NovoRapid, with the corresponding standard errors and 2-sided 95% CIs. These values will be calculated using the observed proportions of patients in the randomization strata and the observed baseline mean HbA1c in the ITT population.

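### As cross-referenced, the SAP's ANCOVA for FPG, mean 24-hour SMPG and postprandial excursions omits the screening-HbA1c stratum that the protocol keeps (minor)

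*SAP*

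**What the plan says.** **Protocol.** Section 11.4.2.2 sends the continuous secondary endpoints through two-part multiple imputation, "followed by a similar ANCOVA model (as described in Section 11.4.2.1". The ANCOVA in 11.4.2.1.1 lists treatment, region with diabetes type, and the screening HbA1c stratum, which carries the qualifier "except when analyzing the change in HbA1c) and prior use of NovoLog/NovoRapid (Yes, No), as well as the continuous fixed covariate of baseline value". So the stratum leaves the model only when the outcome is HbA1c change. The synopsis is broader still: "randomization strata, as well as the continuous fixed covariate of baseline value".

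**SAP.** Section 2.4.4.2.1 covers the same endpoints and refers to the ANCOVA of 2.4.4.1.1: imputation is "followed by a similar ANCOVA model (as described in Section 2.4.4.1.1". The covariate list there ends "US T2DM, Japan T1DM) and prior use of NovoLog/NovoRapid (Yes, No), as well as the continuous fixed covariate of baseline value". It has neither the screening HbA1c stratum nor the exception clause. In 2.4.4.2.1 itself, the step 2 imputation model for treatment completers does keep the protocol's rule: "screening HbA1c (<8%, ≥8%) (except when analyzing the change in HbA1c) and prior use of NovoLog/NovoRapid (Yes, No". Under the heading "STATISTICAL MODIFICATIONS MADE IN THE STATISTICAL ANALYSIS PLAN" (SAP 1.6), the entry is that none applies.

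Both documents stratify the randomization by screening HbA1c (<8.0%, ≥8.0%). SAP 2.4.4.3 treats all secondary efficacy variables as exploratory.

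**The concern.** For change in HbA1c, leaving out the stratum is harmless and follows the protocol, because continuous baseline HbA1c is in the model. For FPG and the SMPG endpoints the baseline covariate is the FPG or SMPG value, so a model built literally from SAP 2.4.4.1.1 has no HbA1c term at all, although the trial was randomized within HbA1c strata.

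Two things are at stake. One is pre-specification: a programmer working from the SAP omits the term, while one working from the protocol includes it, and no entry in the SAP says which is meant. The other is precision: if the stratum predicts later glucose after adjustment for the baseline value, the reported interval is wider than it needs to be. The model is used at Week 26 and Week 52, in the ITT population and separately in T1DM patients.

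**Working it through.** **1. The plan's own figure, for context.** The documents give no precision figure for FPG or SMPG. The only stated power is for the primary test: 290 per arm, SD 1.0%, margin 0.3%, true difference 0, one-sided 0.025. The standard error is 1.0 × √(2/290) = 0.0830, and power = Φ(0.3/0.0830 − 1.96) = 95.1%. Both directions together give 2 × 0.951 − 1 = 90.2%. Both match the plan, and neither uses the FPG/SMPG model.

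**2. Terms in the ANCOVA for FPG and the two SMPG endpoints.**

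| Term | Protocol 11.4.2.1.1 via 11.4.2.2 | SAP 2.4.4.1.1 via 2.4.4.2.1 |
|---|---|---|
| Treatment | yes | yes |
| Region with diabetes type | yes | yes |
| Screening HbA1c stratum | yes | **no** |
| Prior NovoLog/NovoRapid use | yes | yes |
| Baseline of the endpoint | yes | yes |

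The HbA1c endpoints are not affected, since both documents leave the stratum out for them. SMPG by time-point is descriptive only in the SAP, so it is outside this point.

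**3. What the SAP does elsewhere.** The stratum is kept in the models for HbA1c responders (2.4.4.2.2), hypoglycemia incidence and rate (2.4.5.1), and the AIA risk difference and odds ratio (2.4.5.7). The FPG/SMPG ANCOVA is the odd one out, which points to a drafting slip.

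**4. Size.** Let r be the partial correlation of the stratum with the outcome, given the other covariates. The interval without the stratum is wider by the factor 1/√(1 − r²). The documents give no r, so it is assumed:

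| r | Factor | CI wider by |
|---|---|---|
| 0 | 1.000 | 0% |
| 0.1 | 1.005 | 0.5% |
| 0.2 | 1.021 | 2.1% |
| 0.3 | 1.048 | 4.8% |
| 0.4 | 1.091 | 9.1% |

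**5. Bias and coverage.** These were checked by simulating 580 patients, half in each stratum and randomized 1:1 within stratum, with no treatment effect. Baseline = N(0,1) + 0.5 × stratum. Outcome = −0.5 × baseline + g × stratum + N(0,1). There were 3,000 trials for each g.

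| g (residual SDs) | Mean estimate without stratum | Empirical SE with / without | Coverage with / without | CI width ratio |
|---|---|---|---|---|
| 0 | −0.0011 | 0.0843 / 0.0843 | 94.4% / 94.4% | 1.000 |
| 0.3 | −0.0010 | 0.0847 / 0.0847 | 94.6% / 94.7% | 1.011 |
| 0.6 | −0.0010 | 0.0834 / 0.0836 | 95.0% / 95.8% | 1.041 |
| 1.0 | 0.0005 | 0.0833 / 0.0838 | 94.5% / 96.8% | 1.111 |

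The two approaches agree. Here the stratum's variance given baseline is 0.25 × (1 − 0.125²/(0.25 × 1.0625)) = 0.2353, so the expected ratio is √(1 + 0.2353g²) = 1.011, 1.041 and 1.111 for g = 0.3, 0.6 and 1.0. These correspond to r of about 0.14, 0.28 and 0.44.

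Stratified randomization already balances the factor, so the estimate itself hardly varies more without it. What is lost is in the model-based interval, which becomes somewhat too wide.

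**The case against.** The strongest reply is that the SAP never says it drops the stratum. Section 2.4.4.1.1 is written for change in HbA1c, the one outcome for which the protocol also leaves it out. The word *similar* leaves room to restore it, the imputation text repeats the protocol's exception rule, and the nil entry in SAP 1.6 fits a reading in which nothing was meant to change. Much of this stands. A reader might infer a deliberate, concealed departure from the protocol, and the documents do not support that.

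The reply does not settle the model, however. When SAP 2.4.4.1.5 uses the same word with the same cross-reference, it spells out each change to the strata. Section 2.4.4.2.1 spells out changes for the imputation only, and no SAP sentence puts the term back into the ANCOVA.

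A reader might also infer that an imputation model holding a term absent from the analysis model is a fault in itself. It is not. A richer imputation model is accepted practice, and the primary analysis works that way too: Week 12 HbA1c change is in its imputation model and not in its ANCOVA. The stratum also enters only step 2 of Part 2, since Part 1 uses treatment group alone.

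Two further objections stand. The endpoints carry no formal testing, and the size rests on an assumed correlation. For postprandial excursions, which are differences between post- and pre-meal values, it could be close to zero.

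**Conclusion.** The point holds as a minor one. As cross-referenced, the SAP's ANCOVA for change in FPG, mean 24-hour SMPG and postprandial excursions lacks a randomization stratum that the protocol keeps for them, and no modification is recorded. The text comparison is firm; that it is a drafting slip is the probable explanation, not a documented one.

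A reader might suppose that the omission distorts the treatment comparison. It does not: randomization is balanced within the stratum, and the simulated mean estimates lie within 0.002 of zero. Coverage without the stratum ran from about 94% to 97%, so any departure is towards caution. For an assumed partial correlation of 0.1 to 0.3 the interval is about 0.5% to 5% wider. The primary analysis, its power and the HbA1c endpoints are unaffected.

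**What to change.** In SAP 2.4.4.2.1, list the ANCOVA terms instead of relying on the cross-reference: treatment group; region with diabetes type; the screening HbA1c stratum (<8%, ≥8%), omitted only when the outcome is HbA1c change; prior NovoLog/NovoRapid use; and the endpoint's own baseline value. The wording already used there for imputation, "screening HbA1c (<8%, ≥8%) (except when analyzing the change in HbA1c) and prior use of NovoLog/NovoRapid (Yes, No", can be reused. This matches protocol 11.4.2.1.1, so no protocol amendment is needed.

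If the removal was intended, record it with a reason in SAP 1.6. Continuous screening HbA1c should not be substituted for the stratum: it is in neither document's ANCOVA and would be a new departure from the protocol.

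The cost is one sentence and one degree of freedom among about 580 patients.

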2.4.4.2.2 Categorical endpoints

The categorical secondary endpoint HbA1c responders (HbA1c <7%) will be analyzed using a logistic regression model with fixed-effect term for treatment, randomization strata of geographical region and type of diabetes (Europe T1DM, US T1DM, US T2DM, Japan T1DM), screening HbA1c (<8%, \geq 8%), and prior use of NovoLog/NovoRapid (Yes, No). If the logistic model does not converge (e.g., due to sparse data), randomization strata may be removed from the model. Patients without assessment at Week 26 (or Week 52 for the analysis at Week 52) will be considered as failure. Odds-ratios and 95% CI will be presented.

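### The HbA1c <7% responder model leaves out continuous baseline HbA1c; adding it, with a standardised risk difference, is a small, cheap improvement to an exploratory endpoint

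*SAP*

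**What the plan says.** SAP 2.4.4.2.2 states that the responder endpoint "will be analyzed using a logistic regression model with fixed-effect term for treatment", with "randomization strata of geographical region and type of diabetes (Europe T1DM, US T1DM, US T2DM, Japan T1DM), screening HbA1c" in two classes and prior use of NovoLog/NovoRapid as the other terms. Protocol 11.4.2.2 has the same content: "The categorical secondary endpoint (HbA1c responders) will be analyzed using a logistic regression model adjusted on the randomization strata". Three further rules in SAP 2.4.4.2.2 matter here:

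- The reported measure is the odds ratio: "Odds-ratios and 95% CI will be presented".
- Missing outcomes count as non-response: "Patients without assessment at Week 26 (or Week 52 for the analysis at Week 52) will be considered as failure".
- If the fit fails to converge, "randomization strata may be removed from the model". No order of removal is given.

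The primary ANCOVA (SAP 2.4.4.1.1) makes the opposite choice for the same laboratory measurement. It contains region/diabetes type and prior use, "as well as the continuous fixed covariate of baseline value", and it omits the screening HbA1c stratum.

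SAP 2.4.4.3 makes the secondary efficacy variables exploratory, and protocol 11.4.2.2 plans no formal testing of them.

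**The concern.** Exclusion criterion E 02 admits screening HbA1c from 7% to 10%. The responder threshold is 7%, at the lower edge of that range. A patient who enters at 7.1% and one who enters at 7.9% receive the same HbA1c adjustment, although their chances of ending below 7% plainly differ. Within a stratum, this prognostic information goes unused and a chance imbalance between arms is not corrected.

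The plan gives no reason for handling HbA1c one way in the change analysis and another way in the analysis of its dichotomised form. The convergence rule adds a smaller difficulty: screening HbA1c is itself a randomisation stratum, so the fallback could remove the only HbA1c adjustment.

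What is at stake is the efficiency and consistency of one descriptive comparison. The non-inferiority conclusion is not affected.

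**Working it through.** **1. The plan's own figures.** The documents give no power, response rate or precision figure for the responder endpoint. The primary calculation (SAP 1.3: 290 per arm, SD 1.0%, margin 0.3%, true difference 0) reproduces:

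- SE = 1.0 × √(2/290) = 0.0830
- Power in one direction = Φ(0.3/0.0830 − 1.96) = 95.1% (stated: at least 95%)
- Power in both directions = 2 × 0.951 − 1 = 90.2% (stated: at least 90%)

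**2. The two responder models compared** (HbA1c terms only):

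- Plan: logit P(Week 26 HbA1c <7%) = α + β·treatment + γ·[screening ≥8%]
- Amended: the same plus θ·baseline HbA1c
- Standardised risk difference (RD) from either model: predict each patient's response probability under each treatment, average over all patients, and subtract.

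**3. Inputs.** From the documents: N = 580, allocation 1:1, screening HbA1c limited to 7-10%. Assumed, because the documents give no values:

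- true HbA1c mean 8.0%, SD 0.8-0.9 before truncation
- within-patient SD 0.15-0.2
- slope of Week 26 on true baseline 0.4-0.8, residual SD 0.6-0.9
- mean fall 0.35-0.4
- treatment shift 0 or −0.25

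These give control response rates of about 16-23%. Region, diabetes type, prior use and missing outcomes were not simulated. There were 3,000 simulated trials per row.

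**4. Results, plan model → amended model.** The change in RD variance is 1/(relative efficiency) − 1; for example, 1/1.085 − 1 = −7.8%.

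| Slope / residual SD (SD of change) | Shift | SE of log OR | OR | Power | RD variance |
|---|---|---|---|---|---|
| 0.6 / 0.65 (0.73) | 0 | 0.2343 → 0.2394 (+2.2%) | 1.00 → 1.00 | n/a | −3.3% |
| 0.6 / 0.65 (0.73) | −0.25 | 0.2182 → 0.2236 (+2.5%) | 1.90 → 1.96 | 84.4 → 86.1% | −3.6% |
| 0.7 / 0.9 (0.94) | 0 | 0.2060 → 0.2098 (+1.8%) | 1.00 → 1.00 | n/a | −2.5% |
| 0.7 / 0.9 (0.94) | −0.25 | 0.1975 → 0.2015 (+2.0%) | 1.58 → 1.61 | 64.0 → 65.4% | −3.0% |
| 0.4 / 0.8 (0.91) | 0 | 0.2122 → 0.2141 (+0.9%) | 1.00 → 1.00 | n/a | −1.1% |
| 0.4 / 0.8 (0.91) | −0.25 | 0.1998 → 0.2017 (+1.0%) | 1.69 → 1.70 | 75.0 → 75.4% | −1.5% |
| 0.8 / 0.6 (0.63) | 0 | 0.2351 → 0.2454 (+4.4%) | 1.00 → 1.00 | n/a | −7.8% |
| 0.8 / 0.6 (0.63) | −0.25 | 0.2228 → 0.2337 (+4.9%) | 1.93 → 2.05 | 84.2 → 86.8% | −7.6% |

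**5. Reading the table.**

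- The SE of the log odds ratio rises in every row. In the last row the ratio of upper to lower 95% limit, exp(2 × 1.96 × SE), goes from 2.40 to 2.50.
- Power still rises when there is an effect, because the conditional log odds ratio moves away from zero by more than its SE grows. In the last row it goes from 0.657 to 0.717 (+9.1%) against +4.9% for the SE.
- The risk difference is where precision improves, with or without an effect.
- The scenarios whose SD of change (0.91, 0.94) lies closest to the planning SD of 1.0% give the smaller gains: 1.1-3.0% in variance and 0.4-1.4 points of power.
- Replacing the stratum by continuous baseline, instead of adding to it, gives almost the same results. In the last row the SE is 0.2331 against 0.2337, and power is 86.9% against 86.8%.

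**6. Sensitivity.** Further simulations with slopes 0.5-0.8 and residual SD 0.55-0.8 agree in direction. In one set the SE rose by 1.3-4.8%; in another, with different remaining inputs, by 1.7-8.2%. Counting 8% missing as failure reduced the relative efficiency of the risk difference in a middle scenario from 1.033 to 1.021. With no true effect, the log odds ratios from the two models differed by 0.03-0.06 on average within a trial, so within-stratum imbalance does move the estimate, but slightly.

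**The case against.** The best defence is that the model adjusts for every randomisation stratum, which is a standard specification. The protocol and SAP agree on it, and the hypoglycemia and antibody logistic models use the same strata. Continuous baseline is already in the analysis that carries the HbA1c inference. The responder result is descriptive. All of this stands, and it is why the point is minor.

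Three stronger readings are tempting, and none is supported:

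- A reader might infer that the planned odds ratio is less precise than the data allow. For the measure the SAP reports, the reverse holds: a further prognostic covariate in a logistic model widens the interval of the conditional log odds ratio.
- A reader might turn a squared z-ratio of about 1.03-1.08 into extra patients (580 × 0.03 to 580 × 0.08, or 17 to 46). That ratio describes power to reject an odds ratio of 1 when an effect exists. No such test is planned, and the sample-size section assumes a true HbA1c difference of zero.
- A reader might say that the model adjusts for nothing beyond the screening stratum, or that the change is free. Region/diabetes type and prior use are also in the model. The odds ratio is non-collapsible, so conditioning on one more covariate changes the quantity being estimated.

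**Conclusion.** The omission is confirmed in both documents and is worth correcting as a low-priority improvement. Its benefit is better adjustment for within-stratum differences, consistency with the ANCOVA, and a modest efficiency gain. That gain is roughly 1-8% lower variance for a standardised risk difference, and about 0-3 points of power if an effect exists. Against it stand a rise of about 1-5% in the SE of the log odds ratio, somewhat more under the most prognostic inputs tried, and a changed conditional odds ratio.

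These sizes depend on assumed slopes, residual SDs and response rates. They come from models without region, diabetes type and prior use, and counting missing outcomes as failures would probably shrink the gain. The direction of each effect does not depend on the particular values chosen. The case for the change should not be argued as a narrower odds-ratio interval.

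**What to change.** In SAP 2.4.4.2.2, and in protocol 11.4.2.2 if it is amended:

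1. Add continuous baseline HbA1c to the responder model at Week 26 and Week 52, alongside treatment and the randomisation strata.
2. State that this term stays in the model if strata are removed for non-convergence, and give the order in which strata would be removed.
3. Report the baseline-standardised risk difference with 95% CI beside the odds ratio, naming the variance method (for example the delta method or bootstrap). This is where the precision gain appears, so it belongs with the change and should not be left optional.
4. Say that the odds ratio is conditional on baseline HbA1c as well as on the strata.

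The cost is one model term and one derived estimate. No new data are needed: the flow chart schedules central-laboratory HbA1c at both Visit 1 and Visit 3. SAP 2.1.1 takes the last value up to randomisation as baseline and eligibility requires a screening value, so few if any patients should lack the covariate.
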